A pilot study was conducted to compare the effectiveness of pharmacopuncture and physiotherapy in patients with chronic LBP. The between-group difference in the mean reduction of the NRS score for LBP was 1.37 ± 1.94 at the primary endpoint, which is immediately after the 5-week treatment; further, Cohen's d was calculated as 0.71. The correlation between the baseline and endpoint was 0.53. Given a significance of 95% and power of 90%, the sample size was calculated to be 64. Considering a 30% withdrawal rate and the recruitment of participants from four facilities, we aim to recruit 100 patients.

Recruitment

Participants will be recruited using a press release, advertisement posters at the clinical trial facility, and online recruitment sites.

Randomization and Allocation Concealment

A statistician will randomize patients into two groups at the same ratio (50 persons for each) using a randomization table on R studio 1.1.463 (© 2009-2018 R Studio, Inc.). The random sequence will be performed using block randomization; further, the size of each block will be randomly set to 2 or 4. The randomization results will be placed in a sealed opaque envelope and stored in a double-locked cabinet by a third person not involved in the study. The coordinator at each study facility will open the envelope for group allocation. Only participants who provide an ICF will be randomly assigned. The randomization number assigned to each participant will be recorded in the electronic medical record.

Blinding

Since blinding the practitioner administering the treatment and the participants is impossible due to the nature of the intervention, only the outcome assessors will be blinded. Outcome-assessors not involved in the procedure and blinded from the group allocation will perform the assessment before the procedure in an isolated space.

Data Collection and Management

We will use an e-CRF using the Internet-based Clinical Research and Trial management system (iCReaT). The principal investigator will train the outcome assessors and investigators of each facility on the standard operating procedure (SOP) as a reference for the study procedures, including writing a CRF and entering data. A query will be issued for a range check of data values. Data entered into the e-CRF will be cleaned and locked to prevent access by investigators other than the one in charge of data management.

Statistical Methods

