We will perform both intention-to-treat (ITT) and per-protocol (PP) analyses, with ITT as the primary analysis. For the PP analysis, we will include participants who complete at least seven treatment sessions over 5 weeks. Missing data will be handled by multiple imputation (MI) for analysis of covariance (ANCOVA) and comparison of area under the curve (AUC), as well as

the mixed model for repeated measures for the linear mixed model. For survival analysis, outcomes after the missing time point will be censored. For sensitivity analysis, the last observation carried forward (LOCF) will be used for missing data imputation; further, the normality of distribution will be tested. Nonparametric data will be analyzed using the Wilcoxon-rank sum test. Sociodemographic characteristics and treatment expectancy of the participants will be assessed according to the group. Continuous variables will be presented as mean (SD) or median (quartile), with between-group differences being analyzed using Student's t-test or Wilcoxon-rank sum test, depending on their distribution. Categorical variables will be presented as frequency (%) and analyzed with the chi-square test or Fisher's exact test.

The study endpoints are the differences in the extent of changes in continuous outcomes (NRS, VAS, NDI, NPQ, EQ- 5D-5L, SF-12) at each time point from the baseline. As the primary analysis, we will use a linear mixed model with the covariant factors significantly different from the baseline as covariates and the group as the fixed factor. Next, ANCOVA will be performed on sets processed by MI and LOCF.

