To compare the total difference in each outcome within a certain period (treatment period and total study period), the AUC will be calculated for each time point after randomization and compared using Student's t-test. Further, the proportion of patients whose NRS and VAS scores dropped by > 50% from the baseline values will be compared at each time point. The time from randomization to lumbar recovery, which was defined as > 50% reduction in the pain indices, will be compared using Kaplan-Meier survival analysis. Further, the curves will be compared using the Log rank test. Additionally, hazard ratios will be compared using the Cox proportional hazard model. The significance level will be set at 0.05 for all analyses. All statistical analyses will be performed using the SAS 9.4 (© SAS Institute, Inc., Cary, NC, USA) or R studio 1.1.463 (© 2009-2018 RStudio, Inc.) software. Statistical significance will be set at $p < 0.05$.

In case the superiority test fails, a non-inferiority test will be performed. The non-inferiority margin will be set to -1 (NRS), which represents half of the minimal clinically important difference. Pharmacopuncture will be considered non-inferior to physiotherapy if the lower bound of the 95% confidence interval (CI) of the between-group difference of the NRS score reduction does not exceed the non-inferiority margin.

Data Monitoring

The monitoring staff will supervise the clinical trial process, as well as periodically review and confirm whether the study is performed and recorded according to the protocol, SOP, clinical trial management standards, and applicable regulations. The clinical trial will be monitored by the monitoring staff of each clinical trial facility and the sponsor institution using periodic visits and phone calls. At the monitoring visits, the monitoring staff will check the original participant records and data storage (study files). Further, they will inspect the clinical trial procedure and discuss any problems with the investigators.

In case of unexpected or unacceptable risks to participants or occurrence of serious adverse events related to pharmacopuncture or physiotherapy in $\geq 25\%$ of the participants, the clinical trial may be paused. The analysis will be only accessed by the statistician and principal investigator; additionally, the final decision to terminate the study will be made by the principal

investigator

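### As worded, the fallback non-inferiority rule is reversed: a lower confidence bound that does not exceed -1 is a bound at or below -1

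*Combined protocol and SAP*

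**What the plan says.** The last paragraph of Statistical Methods adds a second test: "In case the superiority test fails, a non-inferiority test will be performed". It fixes the threshold: "The non-inferiority margin will be set to -1 (NRS), which represents half of the minimal clinically important difference". It then calls pharmacopuncture non-inferior to physiotherapy if the lower limit of the 95% CI of the "between-group difference of the NRS score reduction does not exceed the non-inferiority margin". No other sentence in the document states a non-inferiority criterion.

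The remaining elements of the test can be found elsewhere. Sample Size Calculation gives the pilot difference in mean NRS reduction as "1.37 ± 1.94 at the primary endpoint, which is immediately after the 5-week treatment", which supplies the scale and the time point. Statistical Methods supplies the primary analysis set: "We will perform both intention-to-treat (ITT) and per-protocol (PP) analyses, with ITT as the primary analysis".

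**The concern.** On the NRS, 0 is no pain and 10 the worst pain, so a larger reduction is better. With a negative margin and a lower bound, the difference has to be pharmacopuncture minus physiotherapy, and non-inferiority is shown when the whole interval lies above -1. The sentence asks instead that the lower bound not exceed -1, which in numerical order means at or below -1. That is the region where a deficit of 1 point or more has not been ruled out.

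Followed literally, the rule would refuse non-inferiority to a treatment that performs like the control and grant it to one that is clearly worse. When superiority has failed, this sentence alone decides whether non-inferiority is claimed.

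**Working it through.** **Inputs**

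- Margin: -1 NRS point (Statistical Methods).
- Planned difference 1.37 and SD 1.94 (Sample Size Calculation).
- Baseline adjustment: "The correlation between the baseline and endpoint was 0.53" (Sample Size Calculation).
- Numbers: 50 per arm (Randomization and Allocation Concealment). The 30% loss comes from "Considering a 30% withdrawal rate and the recruitment of participants from four facilities, we aim to recruit 100 patients", so 50 × 0.70 = 35 per arm.
- Assumptions: difference taken as pharmacopuncture minus physiotherapy; two-sided 5% level; normal approximation for the probabilities.

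**The plan's own figure.** Adjusted SD = 1.94 × √(1 - 0.53²) = 1.645. A two-sample t-test for a difference of 1.37 with 90% power needs 31.3, so 32 per arm, or 64 in total. This matches the stated 64. The inputs are therefore being read as the plan reads them, and the sample size is not in question.

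**The two rules.** Let L be the lower 95% bound.

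- As written: non-inferior if L ≤ -1.
- Valid rule: non-inferior if L > -1.

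These are complements. Reversing the subtraction does not help: the test would then need the *upper* bound to be below +1. No sign convention turns L ≤ -1 into a non-inferiority test.

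**Example intervals, 50 per arm.** SE = SD × √(2/n) = 1.94 × √(2/50) = 0.388; half-width = 1.96 × 0.388 = 0.760. With SD 1.645, SE = 0.329 and half-width = 0.645.

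| Observed difference | CI, SD 1.94 | CI, SD 1.645 | Valid rule | As written |
|---|---|---|---|---|
| 0 | -0.76 to 0.76 | -0.64 to 0.64 | non-inferior | fails |
| -1.5 | -2.26 to -0.74 | -2.14 to -0.86 | fails | non-inferior |

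**Chance of declaring non-inferiority through the fallback.** With true difference δ:

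- As written: P(L ≤ -1) = 1 - Φ((1 + δ)/SE - 1.96).
- Valid rule, after superiority fails: P(-1 < L ≤ 0) = Φ((1 + δ)/SE - 1.96) - Φ(δ/SE - 1.96).

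At δ = -1 the first term is Φ(-1.96), so the result is 97.5% as written and 2.5% under the valid rule in all four cases below. For δ = 0, SD 1.94 and 50 per arm: 1/0.388 - 1.96 = 0.617 and Φ(0.617) = 0.7315. That gives 1 - 0.7315 = 0.2685 as written, and 0.7315 - 0.025 = 0.7065 under the valid rule.

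**How often the fallback is reached.** P(superiority fails) = 1 - Φ(δ/SE - 1.96). For δ = 1.37, SD 1.94 and 50 per arm: 1.37/0.388 - 1.96 = 1.571, giving 0.0581. At δ = 0 it is 0.975 in every case.

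| SD | n per arm | SE | δ = 0, as written | δ = 0, valid rule | Superiority fails at δ = 1.37 |
|---|---|---|---|---|---|
| 1.94 | 50 | 0.388 | 27% | 71% | 5.8% |
| 1.94 | 35 | 0.464 | 42% | 55% | 16.0% |
| 1.645 | 50 | 0.329 | 14% | 83% | 1.4% |
| 1.645 | 35 | 0.393 | 28% | 70% | 6.4% |

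**The case against.** The strongest reply is that *exceed*, applied to a limit, ordinarily means to go past it. A bound that does not go past -1 on the unfavourable side stays above -1, which is the correct rule. The negative margin, the choice of the lower bound and the positive pilot difference all point that way, and the literal reading makes the test absurd because worse results pass more easily. On this view the sentence is loose wording, nobody planned a reversed test, and the 97.5% figure follows by definition from swapping a region for its complement.

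Much of this stands. The intent is recoverable, and nothing suggests that the trial statistician would apply the reversed rule. Every contrast above belongs to the literal reading only. The fallback is seldom reached at the planned effect. The probabilities are illustrative, since the planned primary analysis is a linear mixed model and not a simple two-sample comparison. The subtraction, time point and analysis set are implied elsewhere and are not separate errors.

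None of this makes the sentence correct. With a negative threshold, numerical order and distance from zero give opposite answers, so *exceed* is precisely the word that fails here. A pre-specified criterion should not rely on the reader to supply its direction.

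**Conclusion.** The concern holds. The trial's only stated non-inferiority criterion is, as worded, the complement of a valid one, and following it literally would give the opposite of the intended conclusion. The reversal depends only on numerical order, not on the SD, the numbers analysed or the estimator. The probabilities attached to it rest on the pilot SD (raw or baseline-adjusted), 35 to 50 per arm and a normal approximation.

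This is an error in the statement of the rule, and no evidence that a reversed test was intended. It should be corrected because it matters most where the true difference is near zero: there superiority would almost always fail and the fallback would settle the trial's conclusion. The primary superiority analysis is unaffected.

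**What to change.** Replace the criterion with a sentence such as:

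> Pharmacopuncture is non-inferior if the lower bound of the two-sided 95% CI for the difference in NRS reduction from baseline (pharmacopuncture minus physiotherapy) at the end of the 5-week treatment, in the ITT set, is greater than -1.

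The essential change is *greater than -1*. Naming the subtraction, time point and analysis set merely brings into the rule what the document already implies. Report the PP result, which is already planned, alongside. The cost is one sentence; margin, sample size, conduct and planned analyses stay as they are.
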